#### **10.7. Provision of Study Results to Investigators, Posting of Information on Publicly Available Clinical Trials Registers and Publication**

Where required by applicable regulatory requirements, an Investigator signatory will be identified for the approval of the clinical study report. The Investigator will be provided reasonable access to statistical tables, figures, and relevant reports and will have the opportunity to review the complete study results at a GSK site or other mutually-agreeable location.

GSK will also provide the Investigator with the full summary of the study results. The Investigator is encouraged to share the summary results with the study subjects, as appropriate.

GSK will provide the Investigator with the randomization codes for their site only after completion of the full statistical analysis.

The procedures and timing for public disclosure of the results summary and for development of a manuscript for publication will be in accordance with GSK Policy.

A manuscript will be progressed for publication in the scientific literature if the results provide important scientific or medical knowledge.

## 12. APPENDICES

### 12.1. Appendix 1 – Abbreviations and Trademarks

#### Abbreviations

ACR	American College of Rheumatology
AE	Adverse Event
ALT	Alanine aminotransferase (SGPT)
AMD	Age-related macular degeneration
Anti-CCP	Anti-Cyclic Citrullinated Peptide
Anti-dsDNA	Anti-double stranded deoxyribose nucleic acid
AST	Aspartate aminotransferase (SGOT)
AUC	Area under concentration-time curve
BID	Twice a day
CARLOS	Cartilage Loss Scoring System
CI	Confidence Interval
CKD-EPI	Chronic Kidney Disease Epidemiology Collaboration equation
C max	Maximum observed concentration
CNS	Central nervous system
CONSORT	Consolidated Standards of Reporting Trials
CRF	Case Report Form
CRP	C-Reactive Protein
C-SSRS	Columbia Suicide Severity Rating Scale
CV	Cardiovascular
CYP	Cytochrome P
DAS	Disease Activity Score
DAS28	Disease activity score for 28 different joints
DAS28(CRP)	Disease activity score for 28 different joints with CRP value
DCE	Dynamic contrast enhanced
DNA	Deoxyribose Nucleic Acid
DMARD	Disease-Modifying Antirheumatic Drugs
DPU	Discovery Performance Unit
DRC	Data Review Committee
ECG	Electrocardiogram
EDL	Early Development Lead
EMA	European Medicines Agency
ETCO 2	End-tidal Carbon Dioxide
EULAR	European League Against Rheumatism
FACIT-Fatigue	Functional Assessment of Chronic Illness Therapy-Fatigue
FDA	Food and Drug Administration
FRP	Females of Reproductive Potential
FSH	Follicle Stimulating Hormone
FTiH	First Time in Human
GCP	Good Clinical Practice

Gd	Gadolinium
GEE	Generalised Estimating Equations
GFR	Glomerular Filtrate Rate
GSK	GlaxoSmithKline
HAQ-DI	Disability Index of the Healthy Assessment Questionnaire
HBcAb	Hepatitis B Core Antibody
HBsAg	Hepatitis B Surface Antigen
hCG	Human Chorionic Gonadotropin
HIV	Human Immunodeficiency Virus
HRT	Hormone Replacement Therapy
IB	Investigator Brochure
ICH	International Conference on Harmonisation
IDSL	Integrated Data Standards Library
IEC	Independent Ethics Committee
IL	Interleukin
IP	Investigational Product
IRB	Institutional Review Board
IRE	Initial rate of enhancement
IRTS	Interactive Response Technology System
Kg	Kilogram
L	Litre
LDL	Low Density Lipoprotein
MCH	Mean corpuscular haemoglobin
MCHC	Mean corpuscular haemoglobin concentration
MCV	Mean Corpuscular Volume
MDMA	3,4-methylenedioxy-methamphetamine
ME	Maximal signal intensity enhancement
MedDRA	Medical Dictionary for Regulatory Activity
mg	Milligram
mL	Millilitre
MLKL	Mixed lineage kinase domain-like protein
mm	Millimeter
mmol	Millimole
MMP	Matrix metalloproteinase
MMRM	Mixed-effect Model Repeat Measurements
MRI	Magnetic Resonance Imaging
msec	millisecond
MRP	Myeloid-related Protein
MSDS	Material Safety Data Sheet
MTX	Methotrexate
NF- $\kappa$ B	Nuclear factor kappa-light-chain-enhancer of activated B cells
NHS	National Health Service
NOAEL	No Adverse Effect Level
NONMEM	Non Linear Mixed Effect Model
NRS	Numeric Rating Scale

NSAID	Non-steroidal anti-inflammatory drug
NSF	Nephrogenic Systemic Fibrosis
OMERACT	Outcome Measures in Rheumatology
PBMC	Peripheral blood mononuclear cell
PCR	Polymerase Chain Reaction
PD	Pharmacodynamic
PGA	Physician's Global Assessment of Disease
Pgp	P-glycoprotein
PGx	Pharmacogenetics
PK	Pharmacokinetic
PPD	Tuberculin Purified Protein Derivative
PPL	Project Physician Lead
PRO	Patient Reported Outcome
PRR	Pattern Recognition Receptor
PSRAE	Possible Suicidality Related Adverse Event
PtGA	Patient Global Assessment of Disease
PTS IVIVT	Platform Technology and Science In Vitro/In Vitro Translation
QTc	Electrocardiogram QT interval corrected for heart rate
QTcB	Electrocardiogram QT interval corrected for heart rate using Bazett's formula
QTcF	Electrocardiogram QT interval corrected for heart rate using Fridericia's formula
RA	Rheumatoid Arthritis
R&D	Research and Development
RAP	Reporting and Analysis Plan
RAMRIQ	Rheumatoid arthritis MRI quantitative
RAMRIS	Rheumatoid arthritis MRI scoring system
RBC	Red Blood Cell
RF	Rheumatoid factor
RIP1	Receptor-interacting protein-1
RIP3	Receptor-interacting protein-3
RNA	Ribonucleic Acid
SAE	Serious Adverse Event
SIB	Suicidal Ideation Behaviour
SLE	Systemic lupus erythematosus
SGOT	Serum Glutamic Oxaloacetic Transaminase
SGPT	Serum Glutamic Pyruvic Transaminase
SOP	Standard Operating Procedure
SpO2	Peripheral Capillary Oxygen Saturation
SRM	Study Reference Manual
SRT	Safety Review Team
TB	Tuberculosis
TEAR	Target Engagement Assay RIP1
TID	Three times a day
TIMP	Tissue inhibitor of metalloproteinases

TLR	Toll-like receptor
TNF	Tumor necrosis factor
TTS	Technical Terms of Supply
UK	United Kingdom
ULN	Upper Limit of Normal
VAS	Visual Analogue Scale
VEGF	Vascular endothelial growth factor
WOCP	Women of Child Bearing Potential

### Trademark Information

Trademarks of the GlaxoSmithKline group of companies
NONE

Trademarks not owned by the GlaxoSmithKline group of companies
QuantiFERON
Sugita
Vectra DA

## 12.2. Appendix 2: Liver Safety Required Actions and Follow up Assessments

**Phase II liver chemistry stopping and increased monitoring criteria** have been designed to assure subject safety and evaluate liver event etiology (in alignment with the FDA premarketing clinical liver safety guidance).

<http://www.fda.gov/downloads/Drugs/GuidanceComplianceRegulatoryInformation/Guidances/UCM174090.pdf>.

### Phase II liver chemistry stopping criteria and required follow up assessments

Liver Chemistry Stopping Criteria – Liver Stopping Event	
ALT-absolute	ALT $\geq$ 5xULN
ALT Increase	ALT $\geq$ 3xULN persists for $\geq$ 4 weeks
Bilirubin	ALT $\geq$ 3xULN and bilirubin $\geq$ 2xULN (>35% direct bilirubin)
INR^2	ALT $\geq$ 3xULN and INR>1.5, if INR measured
Cannot Monitor	ALT $\geq$ 3xULN and cannot be monitored weekly for 4 weeks
Symptomatic	ALT $\geq$ 3xULN associated with symptoms (new or worsening) believed to be related to liver injury or hypersensitivity
Required Actions and Follow up Assessments following ANY Liver Stopping Event	
Actions	Follow Up Assessments

 
• Immediately discontinue study treatment
 
• Report the event to GSK within 24 hours
 
• Complete the liver event CRF and complete an SAE data collection tool if the event also meets the criteria for an SAE
 
• Perform liver event follow up assessments
 
• Monitor the subject until liver chemistries resolve, stabilize, or return to within baseline (see MONITORING below)
 
• Do not restart/rechallenge subject with study treatment unless allowed per protocol and GSK Medical Governance approval is granted
 
• If restart/rechallenge not allowed per protocol or not granted, permanently discontinue study
 
	
 
• Viral hepatitis serology
 
• Blood sample for pharmacokinetic (PK) analysis, obtained within 2 days after last dose
 
• Serum creatine phosphokinase (CPK) and lactate dehydrogenase (LDH).
 
• Fractionate bilirubin, if total bilirubin<math>\geq</math>2xULN
 
• Obtain complete blood count with differential to assess eosinophilia
 
• Record the appearance or worsening of clinical symptoms of liver injury, or hypersensitivity, on the AE report form
 
• Record use of concomitant medications
 


treatment and may continue subject in the study for any protocol specified follow up assessments
 
MONITORING:
 
For bilirubin or INR criteria:
 
 
Repeat liver chemistries (include ALT, AST, alkaline phosphatase, bilirubin) and perform liver event follow up assessments within 24 hrs
 
Monitor subjects twice weekly until liver chemistries resolve, stabilize or return to within baseline
 
A specialist or hepatology consultation is recommended
 
 
For All other criteria:
 
 
Repeat liver chemistries (include ALT, AST, alkaline phosphatase, bilirubin) and perform liver event follow up assessments within 24-72 hrs
 
Monitor subjects weekly until liver chemistries resolve, stabilize or return to within baseline
 
	
on the concomitant medications report form including acetaminophen, herbal remedies, other over the counter medications.
 
 
Record alcohol use on the liver event alcohol intake case report form
 
 
For bilirubin or INR criteria:
 
 
Anti-nuclear antibody, anti-smooth muscle antibody, Type 1 anti-liver kidney microsomal antibodies, and quantitative total immunoglobulin G (IgG or gamma globulins).
 
Serum acetaminophen adduct HPLC assay (quantifies potential acetaminophen contribution to liver injury in subjects with definite or likely acetaminophen use in the preceding week [James, 2009]). NOTE: not required in China
 
Liver imaging (ultrasound, magnetic resonance, or computerised tomography) and /or liver biopsy to evaluate liver disease: complete Liver Imaging and/or Liver Biopsy CRF forms.
 

---	--

- Serum bilirubin fractionation should be performed if testing is available. If serum bilirubin fractionation is not immediately available, discontinue study treatment for that subject if ALT  $\geq$  3xULN **and** bilirubin  $\geq$  2xULN.. Additionally, if serum bilirubin fractionation testing is unavailable, **record presence of detectable urinary bilirubin on dipstick**, indicating direct bilirubin elevations and suggesting liver injury.
- All events of ALT  $\geq$  3xULN **and** bilirubin  $\geq$  2xULN (>35% direct bilirubin) or ALT  $\geq$  3xULN **and** INR>1.5, if INR measured which may indicate severe liver injury (possible 'Hy's Law'), **must be reported as an SAE (excluding studies of hepatic impairment or cirrhosis)**; INR measurement is not required and the threshold value stated will not apply to subjects receiving anticoagulants
- New or worsening symptoms believed to be related to liver injury (such as fatigue, nausea, vomiting, right upper quadrant pain or tenderness, or jaundice) or believed to be related to hypersensitivity (such as fever, rash or eosinophilia)
- Includes:Hepatitis A IgM antibody; Hepatitis B surface antigen and Hepatitis B Core Antibody (IgM); Hepatitis C RNA; Cytomegalovirus IgM antibody; Epstein-Barr viral capsid antigen IgM antibody (or if unavailable, obtain heterophile antibody or monospot testing); Hepatitis E IgM antibody
- PK sample may not be required for subjects known to be receiving placebo or non-GSK comparator treatments.) Record the date/time of the PK blood sample draw and the date/time of the last dose of study treatment prior to blood sample draw on the CRF. If the date or time of the last dose is unclear, provide the subject's best approximation. If the date/time of the last dose cannot be approximated OR a PK sample cannot be collected in the time period indicated above, do not obtain a PK sample. Instructions for sample handling and shipping are in the laboratory manual.

**12.3. Appendix 3: Prednisolone Equivalent Dose Table**

Drug Name	Dose Equivalent to 1 mg Oral Prednisone
Cortisone acetate	5 mg
Hydrocortisone	4 mg
Prednisolone	1 mg
Methylprednisolone	0.8 mg
Triamcinolone	0.8 mg
Dexamethasone	0.15 mg

## 12.4. Appendix 4- Genetic Research

### Genetics – Background

Naturally occurring genetic variation may contribute to inter-individual variability in response to medicines, as well as an individual's risk of developing specific diseases. Genetic factors associated with disease characteristics may also be associated with response to therapy, and could help to explain some clinical study outcomes. For example, genetic variants associated with age-related macular degeneration (AMD) are reported to account for much of the risk for the condition [Gorin, 2012] with certain variants reported to influence treatment response [Chen, 2012]. Thus, knowledge of the genetic etiology of disease may better inform understanding of disease and the development of medicines. Additionally, genetic variability may impact the pharmacokinetics (absorption, distribution, metabolism, and elimination), or pharmacodynamics (relationship between concentration and pharmacologic effects or the time course of pharmacologic effects) of a specific medicine and/or clinical outcomes (efficacy and/or safety) observed in a clinical study.

### Genetic Research Objectives and Analyses

The objectives of the genetic research are to investigate the relationship between genetic variants and:

- Response to medicine, including GSK2982772 or any concomitant medicines;
- Rheumatoid arthritis susceptibility, severity, and progression and related conditions

GSK2982772 is a novel first-in-class asset being introduced to patients with moderate to severe RA for the first time. Currently its mechanism of action is not fully characterised nor understood.

Specific genes may be studied that encode the drug targets, or drug mechanism of action pathways, drug metabolizing enzymes, drug transporters or which may underpin adverse events, disease risk or drug response. These candidate genes may include a common set of ADME (Absorption, Distribution, Metabolism and Excretion) genes that are studied to determine the relationship between gene variants or treatment response and/or tolerance. In addition, continuing research may identify other enzymes, transporters, proteins or receptors that may be involved in response to GSK2982772. The genes that may code for these proteins may also be studied. Genome-wide scans involving a large number of polymorphic markers (e.g. single nucleotide polymorphisms) at defined locations in the genome, often correlated with a candidate gene, may be studied to determine the relationship between genetic variants and treatment response or tolerance. This approach is often employed when a definitive candidate gene does not exist and/or the potential genetic effects are not well understood.

Genetic data may be generated while the study is underway or following completion of the study. Genetic analyses will utilize data collected in the study and will be limited to understanding the objectives highlighted above. Analyses may be performed using data from multiple clinical studies to investigate these research objectives.

If applicable and genetic research is conducted, appropriate descriptive and/or statistical analysis methods will be used to evaluate pharmacogenetic data in the context of the other clinical data. A detailed description of any planned analyses will be documented in a Reporting and Analysis Plan (RAP) prior to initiation of the analysis. Planned analyses and results of genetic investigations will be reported either as part of the clinical RAP and study report, or in a separate genetics RAP and report, as appropriate.

### **Study Population**

Any subject who is enrolled in the study can participate in genetic research. Any subject who has received an allogeneic bone marrow transplant must be excluded from the genetic research.

### **Study Assessments and Procedures**

A key component of successful genetic research is the collection of samples during clinical studies. Collection of samples, even when no *a priori* hypothesis has been identified, may enable future genetic analyses to be conducted to help understand variability in disease and medicine response.

- A 6 ml blood sample will be taken for Deoxyribonucleic acid (DNA) extraction. A blood sample is collected at the baseline visit, after the subject has been randomized and provided informed consent for genetic research. Instructions for collection and shipping of the genetic sample are described in the laboratory manual. The DNA from the blood sample may undergo quality control analyses to confirm the integrity of the sample. If there are concerns regarding the quality of the sample, then the sample may be destroyed. The blood sample is taken on a single occasion unless a duplicate sample is required due to an inability to utilize the original sample.

The genetic sample is labelled (or “coded”) with the same study specific number used to label other samples and data in the study. This number can be traced or linked back to the subject by the Investigator or site staff. Coded samples do not carry personal identifiers (such as name or social security number).

The need to conduct PGx analysis may be identified after a study (or set of studies) of GSK2982772 has been completed and the study data reviewed. In some cases, the samples may not be studied.

Samples will be stored securely and may be kept for up to 15 years after the last subject completes the study, or GSK may destroy the samples sooner. GSK or those working with GSK (for example, other researchers) will only use samples collected from the study for the purpose stated in this protocol and in the informed consent form. Samples may be used as part of the development of a companion diagnostic to support the GSK medicinal product.

Subjects can request their sample to be destroyed at any time.

## **Informed Consent**

Subjects who do not wish to participate in the genetic research may still participate in the study. Genetic informed consent must be obtained prior to any blood being taken.

## **Subject Withdrawal from Study**

If a subject who has consented to participate in genetic research withdraws from the clinical study for any reason other than being lost to follow-up, the subject will be given a choice of one of the following options concerning the genetic sample, if already collected:

- Continue to participate in the genetic research in which case the genetic DNA sample is retained.
- Discontinue participation in the genetic research and destroy the genetic DNA sample.

If a subject withdraws consent for genetic research or requests sample destruction for any reason, the Investigator must complete the appropriate documentation to request sample destruction within the timeframe specified by GSK and maintain the documentation in the site study records.

Genotype data may be generated during the study or after completion of the study and may be analysed during the study or stored for future analysis.

- If a subject withdraws consent for genetic research and genotype data has not been analysed, it will not be analysed or used for future research.
- Genetic data that has been analysed at the time of withdrawn consent will continue to be stored and used, as appropriate.

## **Screen and Baseline Failures**

If a sample for genetic research has been collected and it is determined that the subject does not meet the entry criteria for participation in the study, then the Investigator should instruct the subject that their genetic sample will be destroyed. No forms are required to complete this process as it will be completed as part of the consent and sample reconciliation process. In this instance a sample destruction form will not be available to include in the site files.

## **Provision of Study Results and Confidentiality of Subject's Genetic Data**

GSK may summarize the genetic research results in the clinical study report, or separately and may publish the results in scientific journals.

GSK may share genetic research data with other scientists to further scientific understanding in alignment with the informed consent. GSK does not inform the subject, family members, insurers, or employers of individual genotyping results that are not known to be relevant to the subject's medical care at the time of the study, unless required by law. This is due to the fact that the information generated from genetic

studies is generally preliminary in nature, and therefore the significance and scientific validity of the results are undetermined. Further, data generated in a research laboratory may not meet regulatory requirements for inclusion in clinical care.

## 12.5. Appendix 5: Definition of and Procedures for Recording, Evaluating, Follow-Up and Reporting of Adverse Events

### 12.5.1. Definition of Adverse Events

#### Adverse Event Definition:

- An AE is any untoward medical occurrence in a patient or clinical investigation subject, temporally associated with the use of a medicinal product, whether or not considered related to the medicinal product.
- NOTE: An AE can therefore be any unfavorable and unintended sign (including an abnormal laboratory finding), symptom, or disease (new or exacerbated) temporally associated with the use of a medicinal product.

#### Events meeting AE definition include:

- Any abnormal laboratory test results (hematology, clinical chemistry, or urinalysis) or other safety assessments (e.g., ECGs, radiological scans, vital signs measurements), including those that worsen from baseline, and felt to be clinically significant in the medical and scientific judgement of the Investigator.
- Exacerbation of a chronic or intermittent pre-existing condition including either an increase in frequency and/or intensity of the condition.
- New conditions detected or diagnosed after study treatment administration even though it may have been present prior to the start of the study.
- Signs, symptoms, or the clinical sequelae of a suspected interaction.
- Signs, symptoms, or the clinical sequelae of a suspected overdose of either study treatment or a concomitant medication (overdose per se will not be reported as an AE/SAE unless this is an intentional overdose taken with possible suicidal/self-harming intent. This should be reported regardless of sequelae).
- "Lack of efficacy" or "failure of expected pharmacological action" per se will not be reported as an AE or SAE. However, the signs and symptoms and/or clinical sequelae resulting from lack of efficacy will be reported if they fulfil the definition of an AE or SAE.
- The signs and symptoms and/or clinical sequelae resulting from lack of efficacy will be reported if they fulfil the definition of an AE or SAE. Also, "lack of efficacy" or "failure of expected pharmacological action" also constitutes an AE or SAE.

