### Objective(s)/Endpoint(s)

Objectives	Endpoints
Primary	

 
To investigate the safety and tolerability of 60 mg three times daily doses of GSK2982772 in subjects with moderate to severe Rheumatoid Arthritis.
 
	
 
Adverse events.
 
Clinical laboratory values (clinical chemistry, haematology and urinalysis).
 
Vital sign measurements (blood pressure, heart rate, respiratory rate, and body temperature).
 
12-Lead ECG monitoring.
 

Secondary	

 
To investigate the plasma concentrations of GSK2982772 following 60 mg three times daily doses of GSK2982772 in subjects with moderate to severe Rheumatoid Arthritis.
 
	
 
Pre-dose concentrations of GSK2982772 on Days 8 and 43 (Week 6).
 
Post-dose concentrations of GSK2982772 on Days 1, 8, and 43 (Week 6) at 1, 2, 4 and 6 hours.
 
Trough concentrations on Day 85 (Week 12).
 

 
To investigate the effect of 60 mg three times daily doses of GSK2982772 on inflammatory biomarkers in blood subjects with moderate to severe Rheumatoid Arthritis.
 
	
 
Change from baseline in blood inflammatory markers (e.g., may include but not limited to CRP, IL6, MMP-1, MMP-3, MMP-13, TIMP-1, MCP-1, MIF, MRP8/14 and other markers encompassed by Vectra DA).
 

Objectives	Endpoints

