### 7.3.1. Adverse Events (AEs) and Serious Adverse Events (SAEs)

The definitions of an AE or SAE can be found in [Appendix 5](#).

The Investigator and their designees are responsible for detecting, documenting and reporting events that meet the definition of an AE or SAE.

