#### **9.4. Key Elements of Analysis Plan**

##### **9.4.1. Primary Analyses**

All safety evaluations will be based on the Safety population. Clinical interpretation will be based on the review and displays of adverse events, clinical laboratory values, vital sign measurements and 12-lead ECG monitoring.

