**Events NOT meeting definition of an AE include:**

- Any clinically significant abnormal laboratory findings or other abnormal safety assessments which are associated with the underlying disease, unless judged by the Investigator to be more severe than expected for the subject's condition.
- The disease/disorder being studied or expected progression, signs, or symptoms of the disease/disorder being studied, unless more severe than expected for the subject's condition.
- Medical or surgical procedure (e.g., endoscopy, appendectomy): the condition that leads to the procedure is an AE.
- Situations where an untoward medical occurrence did not occur (social and/or convenience admission to a hospital).
- Anticipated day-to-day fluctuations of pre-existing disease(s) or condition(s) present or detected at the start of the study that do not worsen.

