**12.5.2. Definition of Serious Adverse Events**

If an event is not an AE per definition above, then it cannot be an SAE even if serious conditions are met (e.g., hospitalization for signs/symptoms of the disease under study, death due to progression of disease, etc).

**Serious Adverse Event (SAE) is defined as any untoward medical occurrence that, at any dose:****a. Results in death****b. Is life-threatening**

NOTE:

The term 'life-threatening' in the definition of 'serious' refers to an event in which the subject was at risk of death at the time of the event. It does not refer to an event, which hypothetically might have caused death, if it were more severe.

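### Appendix 5 says in consecutive bullets that lack of efficacy as such is not, and then is, an AE or SAE, so sites have two rules for one category of the adverse-event endpoint

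*Protocol*

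**What the plan says.** Section 7.3.1 of the protocol defines no adverse event itself. It states "The definitions of an AE or SAE can be found in" Appendix 5, and makes investigators responsible for detecting, documenting and reporting whatever meets that definition.

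In Appendix 5, section 12.5.1, the list of events that meet the AE definition closes with two bullets on lack of efficacy. The first says "Lack of efficacy' or 'failure of expected pharmacological action' per se will not be reported as an AE or SAE", then adds that what follows from it clinically (signs, symptoms or sequelae) is still reported when it qualifies as an AE or SAE in its own right. The second repeats that last sentence almost word for word and ends: "Also, 'lack of efficacy' or 'failure of expected pharmacological action' also constitutes an AE or SAE".

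The list of events that are not AEs follows directly. It names "The disease/disorder being studied or expected progression, signs, or symptoms of the disease/disorder being studied". An exception is made where the severity goes beyond what would be expected in that subject.

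Section 12.5.2 then makes AE status a precondition for SAE status: "If an event is not an AE per definition above, then it cannot be an SAE even if serious conditions are met".

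"Adverse events" is the first of four primary endpoints in the synopsis and section 3; the others are laboratory values, vital signs and 12-lead ECG. On analysis, section 9.4.1 states: "Clinical interpretation will be based on the review and displays of adverse events, clinical laboratory values, vital sign measurements and 12-lead ECG monitoring".

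**The concern.** Which events count as adverse events is settled at the site, when the case report form is completed. A later analysis plan cannot recover events that a site, following one bullet, never entered. The study is multicentre, and nothing ties either bullet to particular sites, subjects or event types, so two sites could treat the same situation differently and both be within the protocol.

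Section 4.4 justifies the placebo arm partly by its value for judging safety. If the second bullet is applied, part of the AE count records failure to improve rather than harm. Should non-response differ between arms, the AE comparison would carry that difference as well.

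The conflict also reaches expedited reporting, because section 7.3.1.1 requires SAEs to reach the sponsor within 24 hours. It reaches the record of withdrawals too. Section 5.4.1 discontinues study medication in a subject who starts a prohibited RA treatment; whether the lack of efficacy behind that step is also entered as an AE depends on which bullet the site reads.

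**Working it through.** This is mainly a comparison of texts.

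1. **Lack of efficacy as such.** First bullet: not reported as an AE or SAE. Second bullet: constitutes an AE or SAE. The subject is the same and neither carries a qualifier.

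2. **Can both be true?** One might try to separate being an AE from being reported as one. Section 7.3.1 closes that route, since events that meet the definition are to be documented and reported. Under the second bullet lack of efficacy must be reported; under the first it must not.

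3. **Signs, symptoms and sequelae of lack of efficacy.** Both bullets: reported if they meet the definition. No conflict.

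4. **The list of non-AEs.** It excludes expected signs, symptoms and progression of RA. That sits comfortably with the first bullet, but it concerns the disease rather than lack of efficacy as such, and it does not cancel the second bullet's explicit sentence.

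5. **SAE status.** Under section 12.5.2 a non-AE cannot be an SAE. Under the first bullet lack of efficacy as such can never be an SAE; under the second it can.

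6. **Resolution elsewhere.** Section 7.3.1 points only to Appendix 5. The summaries of Amendments 1 to 3 do not mention the AE definition. The revision chronology describes Amendment 4 as restoring laboratory exclusion and haematologic stopping criteria for Germany, again without mention of it.

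**Scale.** The plan gives no figure for this point, and no rate at which lack of efficacy would be entered as an AE. What can be shown is how much one entry matters. Section 9.2.1 takes n = 16 on active TID and n = 8 on placebo. One subject with no other AE, reclassified, changes the proportion with any AE by 1/16 = 6.25 percentage points on active or 1/8 = 12.5 on placebo.

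Table 5 gives the same picture for a particular event type. Its upper limits are the 97.5th percentile of Beta(1 + x, 1 + n − x). For n = 16 this reproduces the table: 19.5% for x = 0, 28.7% for x = 1 and 36.4% for x = 2. These counts show sensitivity only; they do not estimate how many such events would occur.

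**The case against.** The best case on the other side is that this is a narrow drafting slip with limited reach, and much of that stands.

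- The governing definition in section 12.5.1, any untoward medical occurrence temporally associated with the product, is single and consistent. Only one item in the list of examples conflicts. A reader might infer that the whole primary endpoint has two definitions; the documents do not support that, because three of its four components do not depend on this wording.

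- A reader might infer that every non-responder becomes a subject with an AE. Nothing links responder status to AE entry. The sponsor calculates DAS28-CRP and ACR response (section 7.4.2), questionnaires and AE collection are kept independent (section 12.5.4), and open, non-leading questions are preferred for eliciting AEs (section 7.3.1.2). A count of non-responders would therefore be near a ceiling.

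- A reader might infer a bias that makes an effective drug look safer, or a distortion larger than any safety difference the trial could detect. The first needs the drug to work and sites to use the second bullet; the second has no calculation behind it. Section 9.1 plans no formal hypotheses for safety and section 9.2.1 says the study is not powered.

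- AE terms are MedDRA-coded (section 8), so an entry recorded as lack of efficacy could be found and set apart.

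What remains is that two adjacent operative instructions cannot both be followed and nothing shown chooses between them. Coding helps only with events that were entered, not with those a site following the first bullet left out.

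**Conclusion.** The contradiction is real and confined to lack of efficacy, or failure of expected pharmacological action, as such. It affects the adverse-event component of the primary safety endpoint and, through section 12.5.2, the SAE definition. It may produce AE counts that vary by site and, under the second bullet, that partly reflect non-response.

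Size and direction cannot be stated. The documents give neither a rate of lack of efficacy nor the chance that a site would enter it as an AE. Single entries carry weight in groups of about 16 and 8, but the analysis is by review and display, so no error rate, sample size or decision rule changes. It is an internal inconsistency that should be corrected and does not invalidate the primary analysis.

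The conclusion rests on Appendix 5 as it stands in the Amendment 3 text. The Amendment 4 version of that appendix was not available to check; its revision summary suggests the wording is unchanged, but this is not confirmed.

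**What to change.** Reduce the two bullets to one rule:

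- Delete the second bullet in full. Its first sentence duplicates the bullet before it, and its last sentence contradicts that bullet.
- Keep the first bullet, which leaves lack of efficacy as such outside AE reporting while its signs, symptoms and sequelae are reported if they qualify. This agrees with the list of non-AEs, and no reporting of harm is lost.
- Check the same bullets in the Amendment 4 text and make the same change if they appear there.
- Send sites a short clarification, and query any AE entered solely as lack of efficacy or failure of pharmacological action, so that the displays rest on one rule.

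The cost is one deleted bullet, a site letter and a small data query. Design, sample size and analysis are unchanged.
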